## **8. RESEARCH QUESTION AND OBJECTIVES**

The study aims to make safety and effectiveness comparisons between warfarin, dabigatran, and rivaroxaban in routine clinical practice among Japanese NVAF patients with concomitant CAD.

**Primary objective:**

To compare the risk of major bleeding between dabigatran and warfarin, and between rivaroxaban and warfarin, among Japanese NVAF patients with concomitant CAD

**Secondary objective:**

To compare the net clinical benefits of dabigatran vs. warfarin, and rivaroxaban vs. warfarin, among Japanese NVAF patients with concomitant CAD. Specifically, the composite outcome will be used to indicate net clinical benefits.

**Further objective:**

If the required sample size can be fulfilled and the baseline characteristics are balanced between dabigatran and rivaroxaban groups after IPTW adjustment, to compare the safety and net clinical benefits of dabigatran vs rivaroxaban among Japanese NVAF patients with concomitant CAD.

## **9. RESEARCH METHODS**

### **9.1 STUDY DESIGN**

This study will be a non-interventional cohort study based on existing data. Patients meeting the in/exclusion criteria will be selected and will be defined as 3 patient groups:

Group 1: new users of warfarin

Group 2: new users of dabigatran

Group 3: new users of rivaroxaban

Comparative analyses of the study will follow a two-step approach. In the first step, the primary and secondary outcomes, as well as baseline characteristics, will be compared between Group 1&2 and Group 1&3, respectively.

The second step will utilize the estimated results from step one, which are HRs of major bleeding events between Group 1&2 and between Group 1&3 among NVAF patients with concomitant CAD, to carry out a more accurate sample size calculation to compare dabigatran versus rivaroxaban. If feasible, comparisons will be made on the same outcomes as in step one.

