**c37044336-01**

Proprietary confidential information © 2021 Boehringer Ingelheim International GmbH or one or more of its affiliated companies

	
To compare the risk of major bleeding between dabigatran and warfarin, and between rivaroxaban and warfarin, among Japanese NVAF patients with concomitant CAD.
 
Secondary objective:
 
To compare the net clinical benefits of dabigatran vs. warfarin, and rivaroxaban vs. warfarin, among Japanese NVAF patients with concomitant CAD.
 
Further objective:
 
If the required sample size can be fulfilled and the baseline characteristics are balanced between dabigatran and rivaroxaban groups after IPTW adjustment, to compare the safety and net clinical benefits of dabigatran vs rivaroxaban among Japanese NVAF patients with concomitant CAD.

Country(-ies) of study:	Japan
Author:	Observational Study Specialist, [REDACTED]
Marketing authorisation holder(s):	[REDACTED] Phone : [REDACTED] Fax : [REDACTED]
In case of PASS, add: MAH contact person:	[REDACTED]
In case of PASS, add: <EU-QPPV:>	[REDACTED] Phone: [REDACTED] Fax: [REDACTED] 24-hour phone contact: [REDACTED]

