**c37044336-01**

Proprietary confidential information © 2021 Boehringer Ingelheim International GmbH or one or more of its affiliated companies

Name of company: Boehringer Ingelheim			
Name of finished medicinal product: Pradaxa, Xarelto			
Name of active ingredient: Dabigatran, warfarin, rivaroxaban			
Protocol date: Nov. 15th, 2021	Study number: 1160-0308	Version/Revision: 1.0	Version/Revision date: NA
respectively. Next, a sample size calculation using results from step one will be carried out to assess the of comparisons between Group 2 and Group 3. If feasible, comparisons will be made on the same outcomes as in step one.			
Population:	
The study period is from April 18th, 2011 to December 31st, 2020. Patients in the Japan [REDACTED] database during the study period will be identified based on the following in/exclusion criteria:
 
Inclusion Criteria
 

1. <math>\geq 18</math> years of age

2. Has one year of look-back period prior to the index date (defined as the first date of prescription for dabigatran, rivaroxaban, or warfarin during the study period)

3. New users of warfarin, dabigatran, and rivaroxaban, defined as patients without historic use of any oral anticoagulants during the look-back period

4. Has at least 1 diagnosis of NVAF during the look-back period prior to or on the index date

5. Has at least 1 diagnosis of CAD during the look-back period prior to or on the index date

 
Exclusion Criteria
 

1. Diagnosed with end-stage renal disease, or undergo hemodialysis, or experience pregnancy during the study period

2. Initiate warfarin, dabigatran, rivaroxaban due to valvular AF, AF associated with mechanical valve malfunction or mechanical complication of heart valve prosthesis, or rheumatic AF

3. Underwent joint replacement procedures or diagnosed with venous thromboembolism during the look-back period prior to or on the index date

4. Prescribed with more than 1 OAC on the index date

		

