## **9.5 STUDY SIZE**

During the period from April 2011 to December 2020, there are roughly 17000, 11000, and 4000 NVAF adult patients with a medical history of CAD being respectively treated with either warfarin, rivaroxaban or dabigatran as the first OAC (defined as no history of OAC usage during the 12-month look-back period) within the [REDACTED] database.

According to a published paper based on the [REDACTED] database, the mean (standard deviation, SD) treatment duration of different drugs among new user groups ranged from 265 (263.8) to 868 (725) days, with the dabigatran group exposed to the treatment the longest [P20-03503]. According to the same article, the major bleeding rate for AF patients is 1.5 per 100 patient-years. In comparison, AF patients with concomitant CAD are more likely to fall under high or medium/high risk categories of the HAS-BLED score, a predictor of bleeding complications among AF patients, thus increasing the event rate for major bleeding about 2-3 times [P09-11669], [R11-4223]. Therefore, the major bleeding rate is assumed to be rather 3-4.5 per 100 patient-years among Japanese AF+CAD patients in the [REDACTED] database.

Furthermore, previous analysis concluded substantial superiority of dabigatran (HR=0.66, 95% CI 0.529-0.825) and rivaroxaban (HR=0.74, 95% CI 0.618-0.879) over warfarin in major bleeding among AF patients [P09-11669], [R11-4223]. The comparative rates of major bleeding between individual NOAC- and warfarin- treated patients should follow a similar trend among NVAF patients with concomitant CAD.

For dabigatran vs. warfarin, if the HR is assumed to be 0.66 and the average exposure time to be 1 year per patient, an event rate of 3 per 100 patient-years with 80% power will require a total sample size of 6050 patients and 3025 patients for each arm; an event rate of 4.5 per 100 patient-years will require a total sample size of 4040 patients and 2020 patients for each arm. To be conservative, the lower bound is selected and therefore each arm needs around 3025 patients.

Similarly, assuming the HR of rivaroxaban vs. warfarin is 0.74 and the average exposure time to be 1 year per patient, the lower-bound event rate of 3 per 100 patient-years with 80% power will require a total sample size of 9690 patients and 4845 patients for each arm.

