The second step will determine whether the patient characteristics are comparable between dabigatran and rivaroxaban treatment groups and whether there is the required sample size for comparisons between dabigatran- and rivaroxaban-treated groups. If the database can fulfil the sample size requirement, analysis will move forward for comparative analysis between the two NOAC groups.

For each component outcome of all 3 groups, the event-free survival will be plotted with Kaplan-Meier curves after s-IPTW adjustments.

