## **7. RESEARCH METHODS**

### **7.1 STUDY DESIGN**

This study will be a non-interventional cohort study based on existing data, the [REDACTED] [REDACTED] database. It contains comprehensive medical record data, blood test result data and insurance claims data. Patients meeting the in/exclusion criteria will be selected and will be defined as 3 patient groups:

Group 1: new users of warfarin

Group 2: new users of dabigatran

Group 3: new users of rivaroxaban

Comparative analyses of the study will follow a two-step approach. In the first step, the primary and secondary outcomes, as well as baseline characteristics, will be compared between Group 1&2 and Group 1&3, respectively.

The second step will utilize the estimated results from step one, which are HRs of major bleeding events between Group 1&2 and between Group 1&3 among NVAF patients with concomitant CAD, to carry out a more accurate sample size calculation to compare dabigatran versus rivaroxaban. If feasible, comparisons will be made on the same outcomes as in step one.

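### The dabigatran vs rivaroxaban comparison is gated by a sample size built from the observed step-one bleeding HRs, so the gate depends on nearly the same data as the result it controls

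*Protocol*

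**What the plan says.** The head-to-head comparison is a further objective with two conditions: "If the required sample size can be fulfilled and the baseline characteristics are balanced between dabigatran and rivaroxaban groups after IPTW adjustment" (Protocol title page, abstract and section 8; SAP 6).

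The size condition is described in Protocol 9.1, with the same text in SAP 7.1: "The second step will utilize the estimated results from step one, which are HRs of major bleeding events". These HRs, dabigatran vs warfarin and rivaroxaban vs warfarin, are used "to carry out a more accurate sample size calculation to compare dabigatran versus rivaroxaban". The abstract agrees: "a sample size calculation using results from step one will be carried out". Protocol 9.7.1 makes it a go/no-go rule: "If the database can fulfil the sample size requirement, analysis will move forward for comparative analysis between the two NOAC groups".

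The Table 3 notes in Protocol Annex 3 and SAP Annex 5 refer the reader to Protocol 9.5 for whether the sample is sufficient. Section 9.5 sizes only the two warfarin comparisons. Protocol 9.7.2 and SAP 11.2 are redacted.

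**The concern.** In a trial that is still recruiting, a revised sample size changes how many patients are enrolled. Here the extract closes on 31 December 2020 and cannot grow, so the calculation can only decide whether the comparison is produced.

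Its input is not independent of the answer. The two step-one HRs share the warfarin group, and SAP 11.1 fits one multinomial propensity model and one common-support region to all three groups. Dividing one HR by the other therefore gives nearly the direct HR. A large observed difference makes the required size small and opens the gate; a small one closes it.

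At stake is selective reporting of the head-to-head HR. Estimates far from 1 would tend to be released, and estimates compatible with similar bleeding risk would tend not to be formally reported. The same bleeding-based gate also decides whether the net-benefit composite is compared for this pair.

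**Working it through.** **Inputs (Protocol 9.5).** About 4000 dabigatran and 11000 rivaroxaban patients (dabigatran share p = 4/15); 1 year of exposure; 3 per 100 patient-years, taken as the pooled rate; planning HRs 0.66 and 0.74; 20% loss. **Assumed for step two:** ratio of the two HRs, two-sided 0.05 and 80% power, so z = 1.960 + 0.842 = 2.802 and z² = 7.849.

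**1. The plan's own figures.** Events at 1:1 = 4z²/(ln HR)².
- HR 0.66: 4 × 7.849/0.4155² = 181.8 events. Dividing by 0.03 gives 6,061; the plan says "an event rate of 3 per 100 patient-years with 80% power will require a total sample size of 6050 patients". Dividing by 0.045 gives 4,041, against the plan's 4040. Both reproduce.
- HR 0.74: 346.3 events and 11,543 patients, whereas the plan says it "will require a total sample size of 9690 patients and 4845 patients for each arm". This does not reproduce. It is a separate step-one matter and is not used below.

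**2. Is the ratio the same statistic as the direct HR?** In 1,000 simulated three-group data sets (17000/4000/11000, unweighted Cox), the log ratio of the step-one HRs correlated 0.9997 with the direct log HR. The largest gap was 0.017 on the log scale.

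**3. Size needed at the planning ratio.** 0.66/0.74 = 0.892 and ln = −0.1144.
- 1:1: 4 × 7.849/0.1144² ≈ 2,398 events.
- 4:11: 7.849/(0.1956 × 0.1144²) ≈ 3,066 events, with p(1−p) = 0.1956.
- Expected: 15000 × 0.03 = 450 events, or 360 after 20% loss.

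**4. What opens the gate.** With E events available, the requirement is met when |ln HR| ≥ z/√(p(1−p)E).

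| | 450 events | 360 events |
|---|---|---|
| p(1−p)E | 88.0 | 70.4 |
| SE of log HR | 0.107 | 0.119 |
| Opens at HR ≤ | 0.742 | 0.716 |
| Opens at HR ≥ | 1.348 | 1.396 |

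**5. How often, and with what result, if the true HR is 0.892.**
- Normal approximation: 0.1144/SE = 1.073 and 0.960, so P(open) ≈ Φ(1.073 − 2.802) = 4.2% and Φ(0.960 − 2.802) = 3.3%.
- Poisson simulation (1,000,000 unweighted studies): 5.3% and 4.4%, with median reported HR 0.71 and 0.69.

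**6. The direct test at the bound.** The Schoenfeld SE is only approximate there. At HR 0.742, 450 events split into about 95.6 and 354.4, so |Z| = 0.2986/√(1/95.6 + 1/354.4) = 2.59. At 0.716 with 360 events it is 2.56. The filter on the direct test is therefore about 2.5 to 2.6, not 2.8.

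**7. Sensitivity to the assumed rule.**
- An equal-arm rule capped at 4000 per arm is stricter: HR ≤ 0.697 or ≥ 1.436.
- If weighting doubles the variance (assumed), the 4:11 threshold falls to 2.802/√2 = 1.98. If the gate also applies a 1:1 total-N formula, it falls to 1.75, below 1.96.
- Exposure in the cited database study "ranged from 265 (263.8) to 868 (725) days, with the dabigatran group exposed to the treatment the longest". Assuming 868 days for dabigatran and 265 for rivaroxaban, with 3 to 4.5 per 100 patient-years, the lower bound becomes 0.76 to 0.82. The gate then opens in 5.1% to 11.4% of studies, with median HR 0.74 to 0.80.

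**The case against.** The strongest reply is that the filter is constructed here. No visible passage says that the HRs are divided, and the 80% power is stated only for the warfarin comparisons. The redacted Protocol 9.7.2 and SAP 11.2 may define the rule. This stands for every opening rate and median HR above. It does not answer the main point: Protocol 9.1 and SAP 7.1 name observed bleeding HRs as the input, whatever formula follows.

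A second reply is that little is hidden. Both HRs vs warfarin are reported regardless, as are weighted events, person-years and rates with CIs for each drug (Table 3), and Protocol 9.7.1 plots weighted Kaplan-Meier curves for all three groups. A reader could nearly reconstruct the head-to-head point estimate. This also stands; what is lost is mainly the formal HR and CI.

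A third is that a feasibility condition is legitimate when power at the planning ratio is only about 16% to 19% (360 and 450 events). That supports a size condition set in advance, but not one set by the observed effect. The baseline-balance condition leaves the size gate as it is.

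A reader might go further and infer that the head-to-head HR will be published only if significant. The documents do not support this: the rule is unstated, and under some plausible versions (threshold 1.75) non-significant results would also pass. Nor do they support a claim that the primary or secondary analyses are biased, or that unconditional type I error is inflated. Under the illustrated rule the gate opens in only about 0.5% of studies (normal approximation) when the true HR is 1.

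**Conclusion.** The concern holds as a minor point. The printed rule makes formal reporting of the dabigatran vs rivaroxaban HR depend on nearly the same data as the HR itself, and the visible text does not define the calculation.

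If the rule is 80% power on the ratio of the HRs, a released HR would be exaggerated: typically about 0.7 when the truth is 0.892, with the gate opening in about 3% to 5% of studies. These sizes rest on the assumed rule, two-sided 0.05, 4000 vs 11000 patients, 1 year, 3 per 100 patient-years and unweighted variance. The direction does not depend on the exact settings, as long as a larger observed difference lowers the required size. The primary and secondary objectives are untouched.

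**What to change.** Remove the observed step-one HRs from the gate, in one of two ways:

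- **Preferred:** run comparison 3 whatever the step-one HRs show. Handle covariates with ASD above 0.1 by the additional Cox adjustment already planned in Protocol 9.7.1 and SAP 11.1, and report the HR with its 95% CI as an estimate.
- **Alternative:** keep a size gate, but write it into Protocol 9.5 as an event count, an expected CI width or an HR fixed before outcomes are seen.

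State the expected precision at 1 year and 3 per 100 patient-years. Unweighted, the log-HR SE is about 0.11 to 0.12 (upper/lower CI limit ratio 1.5 to 1.6). If weighting doubles the variance (assumed), it is about 0.15 to 0.17 (ratio 1.8 to 1.9).

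Align the wording wherever the condition appears: the Protocol title page, abstract (objective, design and analysis), sections 8, 9.1 and 9.7.1, and the Annex 3 Table 3 note; SAP 6, 7.1 and the Annex 5 Table 3 note. The Cox sentence in SAP 11.1 lists only the two warfarin contrasts, so add dabigatran vs rivaroxaban unless the redacted SAP 11.2 already has it.

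The cost is wording plus the head-to-head Cox models, since the three-group weights and the ASDs for this pair are already planned. The downside is that an imprecise head-to-head CI may be published and must be labelled as such.

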## **9.2 SETTING**

**Study Period:** the entire time period that includes the look-back period, the cohort entry date (drug index date), and follow-up period for the study population. The study period will be from April 18th, 2011 (start of data collection) to December 31st, 2020 (end of data collection).

**Patient Selection Period:** the time period for which patients are eligible to enter the cohort, which is from April 18th, 2012 to December 31st, 2020.

**Cohort Entry Date:** The drug index date, defined as the first date of prescription for dabigatran, rivaroxaban, or warfarin during the patient selection period.

**Look-back Period:** the 365-day period that ends 1 day prior to the cohort entry date. The earliest start date of the look-back period is April 18th, 2011.

**Loss of follow-up:** the last data point available in the database during the study period.

**Follow-Up Period:** the period starting from the cohort entry date (first prescription of the drug of interest) and ending at the earliest occurrence of the following:

- Discontinuation of the index OAC, defined as a continuous gap of 45 days or more between the expected refill date and the actual refill date (discontinuation date defined as 45 days after the expected refill date)
- Switching to another OAC, if the index OAC is discontinued and another OAC is started within 45 days of the expected refill date of the index OAC
- Loss of follow-up
- Occurrence of outcomes of interest (for primary outcome: major bleeding; for secondary outcome: the onset of the first occurring component event; for further outcomes: the respective onset of component events)
- Death (except for analyses for the composite outcome and all-cause mortality as a component outcome)
- End of study period

The notion of enrollment is not defined in [REDACTED]. Therefore, a proxy enrolment criterion defined as start of enrolment = date of first inpatient/outpatient encounter; end of enrolment = date of last inpatient/outpatient encounter will be used. "Enrolment" herein will refer to this proxy enrolment measure. For entry into the study population, patients will be required to have had at least 365 days of enrollment prior to the cohort entry date.

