### **Inclusion Criteria**

1.  $\geq 18$  years of age
2. Has one year of look-back period prior to the index date (defined as the first date of prescription for dabigatran, rivaroxaban, or warfarin during the study period)
3. New users of warfarin, dabigatran, and rivaroxaban, defined as patients without historic use of any oral anticoagulants during the look-back period
4. Has at least 1 diagnosis of NVAF during the look-back period prior to or on the index date
5. Has at least 1 diagnosis of CAD during the look-back period prior to or on the index date

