## **9.9 LIMITATIONS OF THE RESEARCH METHODS**

This is a non-interventional study based on existing data. The data do not include vital signs or laboratory test results (e.g. blood pressure, international normalized ratio values, renal function parameters). Therefore, the study may be subject to potential residual confounding due to the absence of certain key data.

Further, the [REDACTED] database contains around 23% of emergency care hospitals in Japan, which does not form a fully closed healthcare system and therefore could lead to information bias.

Additionally, the mortality is only known for hospitalized patients during hospitalization, thus resulting in inaccurate estimates of the mortality rate.

Due to the above reasons, the study results might not be generalizable to the entire AF patient population in Japan.

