#### **Inclusion Criteria**

1.  $\geq 18$  years of age on index date
2. Has one year of look-back period prior to the index date (defined as the first date of prescription for dabigatran, rivaroxaban, or warfarin during the study period)
3. New users of warfarin, dabigatran, and rivaroxaban, defined as patients without historic use of any oral anticoagulants during the look-back period
4. Has at least 1 diagnosis of NVAF during the look-back period prior to or on the index date
5. Has at least 1 diagnosis of CAD during the look-back period prior to or on the index date

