### **10.2 HANDLING OF MISSING VALUES**

The absence of a code for a condition will be interpreted as an absence of the event. If a study variable is totally missing from a database, it is excluded from the analysis of the pooled data.

If a variable is missing for only some of the patients a missing data category will be added and utilized in the analysis.

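### The one-year look-back can be satisfied without any encounter inside it, so a patient observed only on the index date can enter as a new user with under-recorded covariates

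*Protocol*

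**What the plan says.** Protocol 9.2 replaces enrolment with a proxy: "start of enrolment = date of first inpatient/outpatient encounter; end of enrolment = date of last inpatient/outpatient encounter". The entry rule is that "patients will be required to have had at least 365 days of enrollment prior to the cohort entry date". The look-back itself is "the 365-day period that ends 1 day prior to the cohort entry date".

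New users are "defined as patients without historic use of any oral anticoagulants during the look-back period" (Protocol 9.2.2, repeated in SAP 7.3). The CAD criterion reads "Has at least 1 diagnosis of CAD during the look-back period prior to or on the index date", and the NVAF criterion takes the same form. Under Protocol 9.3.3, comorbidities, co-medications and procedures count if recorded in the look-back or on the index date.

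SAP 10.2 states: "The absence of a code for a condition will be interpreted as an absence of the event". Protocol 9.9 accepts that the database "does not form a fully closed healthcare system and therefore could lead to information bias", but does not connect this to the new-user definition.

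**The concern.** A new-user design depends on the look-back being observed. Here the proxy shows only that a patient had been seen at some time a year or more before index. It does not show that anything could have been recorded during the year that defines new use and baseline history.

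Two things follow for a patient with an empty look-back:

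- **Covariates.** Bleeding history, other comorbidity and co-medication are counted only if recorded on the index day. Bleeding history also feeds HAS-BLED (SAP 8.3). Antiplatelet duration runs from the earliest prescription in the look-back (SAP Annex 4), so a long-term user seen only at index falls under less than one month or none. Duration is the one antiplatelet variable kept in the propensity model (SAP 11.1). Standardized differences compare recorded values and would not reveal the problem.
- **New-user status.** Anticoagulant supplied outside the participating hospitals during that year leaves no record, and the patient is classed as a starter.

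At stake are the two primary hazard ratios for major bleeding, since continuing users may already have passed any early period of higher bleeding risk.

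**Working it through.** **Step 1. Does the rule guarantee an observed look-back?** Take an index date of 1 June 2016 and a single earlier encounter.

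| Sole earlier encounter | Days before index | At least 365? | Encounter in days -365 to -1? |
|---|---|---|---|
| 3 June 2015 | 364 | No | Yes |
| 2 June 2015 | 365 | Yes | Yes, on its first day only |
| 1 March 2014 | 823 | Yes | No |
| 5 January 2009 | 2704 | Yes, if records before the study period count | No |

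The patient first seen on 1 March 2014 meets the enrolment rule, has no recorded anticoagulant in the look-back, and can meet the NVAF and CAD criteria with codes entered on 1 June 2016. SAP 7.2 and 7.3 repeat these rules and add no activity check. SAP 10.2 then treats unrecorded conditions as absent, not as missing.

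**Step 2. What could hidden continuing users do to a hazard ratio?** The documents give no figure, so every input except the HRs of 0.66 and 0.74 (Protocol 9.5) is an assumption. Let w and p be the shares of hidden continuing users in the warfarin and NOAC groups, and r their bleeding rate relative to true starters. Ignoring weighting,

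observed HR ≈ true HR × [(1 − p) + p·r] / [(1 − w) + w·r].

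| w | p | r | Factor | 0.66 becomes | 0.74 becomes |
|---|---|---|---|---|---|
| 10% | 0 | 0.7 | 1/0.97 | 0.680 | 0.763 |
| 10% | 0 | 0.5 | 1/0.95 | 0.695 | 0.779 |
| 20% | 0 | 0.5 | 1/0.90 | 0.733 | 0.822 |
| 20% | 10% | 0.5 | 0.95/0.90 | 0.697 | 0.781 |
| 10% | 10% | any | 1 | 0.660 | 0.740 |
| 0 | 10% | 0.5 | 0.95 | 0.627 | 0.703 |
| 0 | 20% | 0.5 | 0.90 | 0.594 | 0.666 |

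With p = 0, w from 5% to 30% and r from 0.5 to 0.9, 0.66 becomes 0.66 to 0.78 and 0.74 becomes 0.74 to 0.87. The direction reverses when the hidden users sit in the NOAC group, and the effect vanishes when the shares are equal. Under-recording of covariates is a separate matter that this formula does not capture.

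**Step 3. Could a restricted subset still be informative?** The plan's dabigatran figure comes first. With two-sided 5% (assumed from the 95% CIs), 80% power and 1:1 groups, Schoenfeld events are 4 × (1.960 + 0.842)² / (ln 0.66)² = 181.8. Then 181.8 / 0.03 = 6061, against 6050 in Protocol 9.5. The loss allowance gives 3025 / 0.8 = 3781, as stated. Against about 4000 dabigatran patients the margin is 219, or 5.5%.

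That margin presumes equal groups, but about 17000 warfarin patients are expected. Schoenfeld information is proportional to n₁n₂/(n₁ + n₂), and the plan needs 3025/2 = 1512.5. After 20% loss the database offers 0.8 × 4000 × 17000 / 21000 = 2590. If a share s had no look-back encounter in both groups, 2590 × (1 − s) ≥ 1512.5 gives s ≤ 42%. This ignores variance added by the weights and takes the approximate counts at face value.

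**The case against.** The strongest reply has four parts.

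1. **Covariates are not blank.** Every entrant carries NVAF and CAD codes at least on the index date. Other conditions and drugs recorded that day count, age and sex are known for all, and both risk scores include the index date. A reader might infer that these patients enter with no comorbidity and look healthy to the propensity model. The documents do not support that: recording is thinner, not nil. This part stands.
2. **The index date gives some protection.** It is the first prescription of any of the three study drugs in the selection period (Protocol 9.2), so someone with such a record in that period is indexed then and cannot reappear years later as a starter. A hidden continuing user therefore needs supply outside the database followed by a prescription inside it. A reader might infer that the cohort is known to contain continuing warfarin users and that the NOACs will look worse for it. The documents show neither; entry is possible, with unknown frequency and direction. This part stands.
3. **A stricter entry rule has its own cost.** It would drop genuine starters first seen at index. It would not exclude someone who takes outside warfarin and had an unrelated visit during the year. This stands, and is a reason not to alter the main cohort.
4. **Some analysis text is redacted.** The protocol's checklist places sensitivity analyses in section 9.7.2, which is blacked out, and the data management plan is a separate document. The visible analyses are 1:1 propensity matching (Protocol abstract) and a three-year follow-up limit (SAP 11.1), and neither touches the look-back. No claim is made about what the redacted text contains.

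None of this removes the central fact that the visible rules allow a wholly unobserved look-back year. The general limitation in Protocol 9.9 neither measures nor tests it.

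**Conclusion.** The concern holds as a gap in the definition. The enrolment proxy does not ensure observation during the look-back, so a patient observed only on the index date can be classed as a new user with under-recorded history, and some such patients may be prevalent users treated elsewhere.

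The effect on either primary HR cannot be computed from the documents. The illustrative shifts rest on assumed shares and an assumed relative bleeding rate, and depend on how these patients divide between the drugs. The finding justifies a count and a sensitivity analysis. It does not show that the planned HRs are biased in a known direction.

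**What to change.** Keep the main cohort and the inclusion criteria as they are, and make two additions:

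- **SAP 11.1:** a prespecified sensitivity analysis repeating both primary s-IPTW hazard ratios (dabigatran vs warfarin, rivaroxaban vs warfarin) in patients with one or more inpatient or outpatient encounters from day -365 to day -1. Re-estimate the generalized propensity score and the weights within that subset. Any encounter in the database should qualify: Protocol 9.4 describes one patient ID linking all records, so there is no stated basis for requiring the same hospital.
- **SAP Annex 5, Table 1:** a row giving the number of patients with no look-back encounter, by drug.

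If a redacted section already contains such an analysis, only the table row is needed. Similar HRs in the subset would ease the concern without excluding outside supply; clearly different HRs should be reported beside the main result.

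The cost is a little more analysis work on existing data. The subset will be smaller and less precise, and will omit some genuine starters first seen at index, which is why it belongs in a sensitivity analysis.
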